8. CLINICAL ASSESSMENTS/EXAMINATION PROCEDURES

The ophthalmic examinations listed below will be conducted in the surgery eye (study eye) and in the order specified. The fellow eye (non-study eye) may be examined at the investigators' discretion.

Subject Assessment of Pain via Diary: Surgery eye (study eye) pain will be evaluated prior to each study drug dose using a pain scale included in the dosing and pain assessment diary that subjects complete at home.

Investigator Assessments include the following:

Visual Analog Scale (VAS) (ocular symptoms): Eye pain/discomfort will be evaluated at Screening Visit 1 (Day -14 to Day -2) and at Visit 3 through Visit 7 (Day 1 through Day 32) using a VAS, scoring from 0 to 100 using a mark on a 100 mm line (0 = absent; 100 = maximum).

Best-Corrected Visual Acuity (BCVA): BCVA will be measured at Screening Visit 1 (Day -14 to Day-2) and at Visit 3 through Visit 7 (Day 1 through Day 32) (log of the minimum angle of resolution [logMAR] score using ETDRS [Early Treatment Diabetic Retinopathy Study] chart will be used to measure BCVA). A pinhole test may be performed at Visit 3 (Day 1).

Biomicroscopy: Slit lamp biomicroscopy, including the evaluation of anterior chamber cell (ACC) and anterior chamber flare, chemosis, bulbar conjunctival injection, ciliary injection, corneal edema, and keratic precipitates will be conducted by a board-certified ophthalmologist at Screening Visit 1 (Day -14 to Day -2) and at Visit 3 through Visit 7 (Day 1 through Day 32).

Ophthalmoscopy: Ophthalmoscopy will be performed at Screening Visit 1 (Day -14 to Day-2) and Visit 5 (Day 15) by a board-certified ophthalmologist. Ophthalmoscopy will be performed at Visit 7/Early Discontinuation Visit only if not performed at Visit 5.

Intraocular Pressure (IOP): IOP will be measured at Screening Visit 1 (Day -14 to Day-2) and at Visit 3 through Visit 7 (Day 1 through Day 32) in mmHg using a Goldmann applanation tonometer.

Standard examinations for subjects undergoing cataract surgery will be conducted by the investigator or qualified designated staff. However, ophthalmoscopy and biomicroscopy examinations will be performed by the same board-certified ophthalmologist who performs a subject's cataract surgery. All ratings and procedures should be performed by the same examiner from visit to visit whenever possible.

Adverse Events and Concomitant Medications: At each study visit, subjects will be queried for new adverse events and, if applicable, previously unresolved adverse events. Also, concomitant medications will be documented.

Diary: At Visit 2 through Visit 5 (Day 0 through Day 15), subjects' diaries will be reviewed and compliance with study drug dosing and completion of pain assessments will be evaluated.

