15. Subject has active corneal, conjunctival or canalicular pathology (including ocular infection [bacterial, viral or fungal]) in the study eye. Specifically, active viral diseases of the cornea and conjunctiva including epithelial herpes simplex keratitis (dendritic keratitis), vaccinia, and varicella, and also in mycobacterial infection of the eye and fungal diseases of the ocular structures (such as fungal keratitis).
16. Subject has thinning of the cornea or sclera.
17. Subject plans to undergo uncomplicated unilateral cataract surgery with the aid of anterior capsular staining products (e.g., Trypan blue) or with the aid of a femto (femtosecond) laser.
18. Subject has undergone anti-neoplastic therapy within the last 2 years prior to Screening or plans to undergo anti-neoplastic therapy during the study period.
19. Subject has a history of use of medications to treat benign prostatic hyperplasia that, in the opinion of the investigator, limits adequate dilation of the pupil to safely perform uncomplicated cataract removal and IOL implantation.
20. Subject has a history of liver disease within the last 5 years prior to Screening.
21. Subject has a history of previous ocular trauma in the study eye that places the study eye at risk of increased post-surgical complications or inflammation.
22. Subject has or had a known blood dyscrasia or bone marrow suppression.

23. Subject has an active or chronic/recurrent ocular or systemic disease that is not controlled and may have an impact on wound healing (e.g., diabetes mellitus, systemic connective tissue disease, severe atopic disease).
24. Subject is suffering from alcohol and/or drug abuse.
25. Subject has a known hypersensitivity or poor tolerance to betamethasone and/or betamethasone sodium phosphate or any component of the study drug or any of the procedural medications such as anesthetic and/or fluorescein drops, dilating drops, etc.
26. Female subjects who are currently pregnant or nursing or are planning to become pregnant during the study or have a positive pregnancy test.
27. Subject has previously participated in this study protocol.
28. Subject used (within 30 days of initiation of study treatment) or is anticipating concurrent use of an investigational drug or device.
29. Subject has a condition or a situation which, in the investigator's opinion, might put the subject at increased risk, confound the study data or interfere significantly with the subject's study participation.

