BCVA: A worsening of 3 lines or more in log of the minimum angle of resolution (logMAR) score in the study eye from baseline or any prior visit should be captured in the source documents and on the appropriate case report form as an AE.

IOP: An increase from baseline or any prior study visit of 10 millimeters of mercury (mmHg) in IOP in the study eye should be captured in the source documents and on the appropriate eCRF as an AE. An IOP of 30 mmHg or higher will be reported as an SAE.

Biomicroscopy: Anterior chamber cell and flare, chemosis, bulbar conjunctival injection, ciliary injection, corneal edema, and keratic precipitates will be assessed in the study. Since the severity of these assessments will be recorded and carefully monitored during the study, worsenings do not need to be recorded as AEs unless the investigator judges it appropriate. Any treatment-emergent findings (i.e., findings that were not present prior to treatment or a worsening relative to the pretreatment baseline) outside of these assessments should be recorded as an AE.

Ophthalmoscopy: A new finding or a significant worsening (2 units or more) from baseline should be recorded as an AE.

VAS: Pain/discomfort will be assessed in the study eye. Since the severity of these assessments will be recorded and carefully monitored during the study, worsenings do not need to be recorded as AEs unless the investigator judges it appropriate.

AE Considerations: Additional exams may be scheduled as necessary to ensure the safety of the subjects during the study period. Subjects discontinued due to an AE should be seen for post-study follow-up visits, as needed. Adverse events considered related to study drug that have not resolved or stabilized by the final study visit will be followed during post-study follow-up visits at the discretion of the investigator until the incident has resolved or stabilized and will be documented in the source documents and AE eCRF. Where appropriate, additional written reports and documentation will be provided. Adverse events considered not related to study drug that have not resolved or stabilized by the final study visit will be noted as ongoing in the eCRF, followed at the discretion of the investigator, and recorded in the source documents.

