10.5. Statistical Methods: General Principles

All data processing, summarization and analyses will be performed using Sponsor designee’s SAS Environment / Version 9.4 (or later) of the SAS® statistical software package. The principles that will be applied to all tables, listings and figures (TLFs) unless otherwise stated are outlined in Table 1.

Table 1: Principles for All TLFs

Principle	Value
Baseline	Defined as the last measurement taken prior to dosing (Day -14 to Day -2).
Significant tests	Two-sided and use a 5% significance level for main effects and 10% significance level for interaction terms.
Treatment group labels and order presented	SURF-201 Vehicle
Tables	Data in summary tables presented by treatment group, assessment and visit (where applicable).
Listings	All data collected presented by treatment group, site, subject number, and visit (where applicable), unless otherwise specified.
Descriptive summary statistics for continuous variables	Number of subjects/observations (N), mean, standard deviation (SD), median, minimum (min) and maximum (max).
Descriptive summary statistics for categorical variables	Frequency counts and percentages [n (%)]
Denominator for percentages	Number of subjects in the analysis population, unless stated otherwise
Include “Missing” as category	No, N will change, unless stated otherwise
Display for 0 percentages	-
Display to one more decimal place than collected value	Mean Standard Error Mean Difference Median
Display to two more decimal places than collected value	Standard Deviation Confidence Interval
Date Format	DD-MMM-YYYY

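### The mandated examination order puts tonometry after ophthalmoscopy, so Screening and Day 15 IOP are taken under different conditions from Days 1, 8, 22 and usually 32

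*Combined protocol and SAP*

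**What the plan says.** Section 8 (Clinical Assessments/Examination Procedures) fixes the sequence: "The ophthalmic examinations listed below will be conducted in the surgery eye (study eye) and in the order specified". After the home diary, the list runs VAS, BCVA, biomicroscopy, ophthalmoscopy, IOP.

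The two schedules differ. For the fundus examination: "Ophthalmoscopy will be performed at Screening Visit 1 (Day -14 to Day-2) and Visit 5 (Day 15) by a board-certified ophthalmologist", and "Ophthalmoscopy will be performed at Visit 7/Early Discontinuation Visit only if not performed at Visit 5". For pressure: "IOP will be measured at Screening Visit 1 (Day -14 to Day-2) and at Visit 3 through Visit 7 (Day 1 through Day 32", taken "in mmHg using a Goldmann applanation tonometer".

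The Screening pressure has several uses. Inclusion criterion 5 (Section 4.1) requires it to be above 8 and at most 22 mmHg. Table 1 (Section 10.5) makes it the baseline: "Defined as the last measurement taken prior to dosing (Day -14 to Day -2". Section 9 uses it as one reference for the adverse event trigger: "An increase from baseline or any prior study visit of 10 millimeters of mercury (mmHg) in IOP in the study eye". Section 9 also makes any IOP of 30 mmHg or more an SAE.

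On dilation, exclusion 25 (Section 4.2) refers to hypersensitivity to "any of the procedural medications such as anesthetic and/or fluorescein drops, dilating drops, etc". Nothing ties those drops to ophthalmoscopy, sets an interval between ophthalmoscopy and tonometry, or asks for IOP before dilation.

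**The concern.** A site that follows Section 8 to the letter measures IOP after ophthalmoscopy at two of the six scheduled readings and without it at the other four. If the preceding examination moves the pressure, changes across those visits mix a true change with a change in measurement conditions.

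IOP increase is the first effect of prolonged corticosteroid use listed in Section 6. Ocular safety is the first item in the study objective, and change in IOP is a named safety parameter in Section 2. The adverse event rule is applied subject by subject at a fixed 10 mmHg, so a shift shared by both arms does not drop out of it. A raised Screening value makes a later true rise harder to detect against baseline. A raised Day 15 value can look like a rise from Day 1 or Day 8, because the rule also looks back to every earlier visit. A lowering effect would do the reverse.

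**Working it through.** The plan gives no figure to reproduce: no IOP standard deviation, no effect of ophthalmoscopy, no power for IOP. The sequence comes from the text. Every value of the shift d, the true rise and the SD below is assumed.

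**Step 1. Conditions by visit, from Section 8.**

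| IOP reading | Ophthalmoscopy first? | Shift in reading |
|---|---|---|
| Screening (entry value, baseline) | yes | d |
| Day 1 | no | 0 |
| Day 8 | no | 0 |
| Day 15 | yes | d |
| Day 22 | no | 0 |
| Day 32 | only if missed at Visit 5 | usually 0 |

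**Step 2. Mean change.** Change from baseline at Days 1, 8, 22 and usually 32 moves by 0 − d = −d in each arm. At Day 15 it moves by d − d = 0. With the same d in both arms, the between-arm difference moves by (−d) − (−d) = 0. A simulation with a true difference of 2.0 mmHg and d = 0, 2 and 5 gave differences of 1.98 to 2.02 at Day 8 and 2.00 to 2.01 at Day 15.

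**Step 3. The 10 mmHg rule, one baseline comparison only.** At a visit without ophthalmoscopy, P(trigger) = Φ(−(10 + d − μ)/SD), where μ is the mean true change.

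| μ, SD (mmHg) | d = 0 | d = 1 | d = 2 | d = 3 |
|---|---|---|---|---|
| 4, 4 | 6.68% | 4.01% | 2.28% | 1.22% |
| 4, 5 | 11.51% | 8.08% | 5.48% | 3.59% |

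For example, with μ = 4, SD = 4 and d = 2: Φ(−8/4) = 2.28%. In 40 subjects the first row is 2.7, 1.6, 0.9 and 0.5 expected events. The direction matters: with μ = 2 and SD = 4 the probability is 2.28% at d = 0 and 0.62% at d = +2, but 6.68% at d = −2.

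**Step 4. The full rule.** Section 9 also triggers on a rise from any prior visit, so Step 3 is not the loss of reported events. The full rule was simulated over the five post-baseline readings. Visit errors were independent and normal with SD 4/√2 or 5/√2, so that a difference of two readings has SD 4 or 5. The shift d was added at Screening and Day 15. Subjects with at least one trigger:

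| True rise of 4 mmHg, SD of change | d = 0 | d = 1 | d = 2 | d = 3 |
|---|---|---|---|---|
| from Day 8 onward, SD 4 | 31.9% | 30.3% | 31.4% | 35.0% |
| from Day 1 onward, SD 4 | 23.8% | 18.8% | 16.3% | 16.1% |
| from Day 8 onward, SD 5 | 48.8% | 47.0% | 47.0% | 48.9% |
| from Day 1 onward, SD 5 | 40.3% | 35.6% | 32.9% | 32.2% |

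The largest relative gain is 35.0/31.9 − 1 = +10%. The largest relative loss is 1 − 16.1/23.8 = 32%, which in 40 subjects is 40 × (0.238 − 0.161) = about 3. These are net counts: missed triggers against baseline are partly offset by false triggers at Day 15.

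**Step 5. Fixed limits.** With d > 0, an eye whose unshifted pressure lies between 22 − d and 22 fails the upper entry limit, and one between 8 − d and 8 passes the lower one. With d < 0 an eye somewhat above 22 could be admitted. The 30 mmHg SAE limit is exposed at Day 15 but not at visits without ophthalmoscopy.

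**The case against.** The strongest reply is that the mechanism is not in the documents. No section says ophthalmoscopy is done through a dilated pupil. Exclusion 25 is a hypersensitivity list, and exclusion 19 links pupil dilation to the surgery itself, which is enough to explain why dilating drops are named. Nor do the documents attribute any IOP effect to the examination. If d is zero, nothing changes. This stands, and it limits the point to a possible inconsistency. It does not remove it: the plan leaves sites free to dilate or not, and the mandated order puts tonometry last either way.

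Three stronger readings are tempting.

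- **A reader might infer that the order biases the comparison of SURF-201 with vehicle.** It does not bias the difference in mean change: both masked arms follow the same sequence and a common shift cancels.
- **A reader might infer that the end-of-dosing change, Screening to Day 15, is distorted.** Both readings follow ophthalmoscopy, so the sequence is like-for-like. An argument that the shift differs before and after lens replacement has no support in the documents.
- **A reader might infer from Step 3 that about 30% to 80% of IOP adverse events would be missed.** The arithmetic is right for one comparison with baseline (1 − 8.08/11.51 = 30%; 1 − 1.22/6.68 = 82%). But the rule also looks back to prior visits, including Days 1 and 8, which do not follow ophthalmoscopy, so that range is not the loss in reported events.

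It is also fair to say that IOP is a safety variable rather than an efficacy endpoint, and that the numbers at stake are a few subjects per arm.

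**Conclusion.** The point holds as one of measurement consistency. The mandated order makes the conditions of tonometry differ between Screening and Day 15 on one side and Days 1, 8, 22 and usually 32 on the other. What is exposed is within-arm change across those visits, the per-subject 10 mmHg rule, and readings against the fixed entry and SAE limits.

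The size is conditional. It rests on an assumed upward shift of 1 to 3 mmHg common to both arms, an assumed true rise of 4 mmHg, an SD of change of 4 or 5 mmHg, independent visit errors and ophthalmoscopy done at Visit 5 as scheduled. Under these the net effect on subjects meeting the full rule lies between a slight gain and about a one-third loss, depending mainly on when the rise begins. The documents establish neither the shift nor its sign, so this is not a demonstrated bias. It is a free improvement to a safety measure that matters for a corticosteroid.

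**What to change.** In Section 8, list IOP after biomicroscopy and before ophthalmoscopy, and state that IOP is measured before any dilating drop at every visit. All six readings then stand at the same point in the sequence (d = 0 throughout), whether or not a site dilates for ophthalmoscopy. Biomicroscopy, which supplies the ACC grade for the primary endpoint, stays ahead of tonometry as it is now.

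The cost is reordering two paragraphs and the matching visit worksheet. No procedure, visit or staff is added.

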9. ADVERSE EVENTS

Throughout the course of the study, the investigator must remain alert to possible adverse events or untoward findings. If adverse events occur, the first concern will be the safety of the subject. Appropriate medical intervention will be provided by the investigator.

Adverse Event (AE) Definition: An AE is any untoward medical occurrence associated with the use of a study drug in a clinical investigation subject, whether or not considered related to the study drug.

Adverse Event Reporting Period: The AE reporting period for this trial begins upon signing the ICF and ends at the completion of the subjects' final study visit exam. All AEs reported by the subject during the course of the study, or elicited by questions from the investigator, or noted as a result of procedures carried out on the subject, during the AE-reporting period must be recorded by site staff in the source documents and on the AE eCRF, whether or not the event is considered related to the study drug. In addition, any known untoward event that occurs subsequent to the AE reporting period that the investigator assesses as related to the study drug should also be reported as an AE.

Serious Adverse Event (SAE) Definition: A serious adverse event (SAE) or reaction is any untoward medical occurrence that at any dose:

- Results in death
- Is immediately life-threatening or immediately sight-threatening in the study eye (surgery eye)
- Requires inpatient hospitalization or prolongation of existing hospitalization
- Results in persistent or significant incapacity or substantial disruption of the ability to conduct normal life functions
- Is a congenital anomaly/birth defect
- Is an important medical event that may jeopardize the subject or may require medical intervention to prevent one of the outcomes listed above

SAE Reporting: SAEs must be immediately reported (within 24 hours of awareness of the event) to designated CRO and will be clearly documented in the source documents and on the appropriate AE eCRF and SAE Report Form. The investigator must also notify the IRB of any SAEs, according to the IRB's guidelines.

Pre-existing Conditions: In this trial, a pre-existing condition (i.e., a disorder present before the AE-reporting period started and noted on the Systemic and/or Ocular Medical History Forms) should not be reported as an AE unless the condition worsens or episodes increase in frequency or severity during the AE-reporting period.

BCVA: A worsening of 3 lines or more in log of the minimum angle of resolution (logMAR) score in the study eye from baseline or any prior visit should be captured in the source documents and on the appropriate case report form as an AE.

IOP: An increase from baseline or any prior study visit of 10 millimeters of mercury (mmHg) in IOP in the study eye should be captured in the source documents and on the appropriate eCRF as an AE. An IOP of 30 mmHg or higher will be reported as an SAE.

Biomicroscopy: Anterior chamber cell and flare, chemosis, bulbar conjunctival injection, ciliary injection, corneal edema, and keratic precipitates will be assessed in the study. Since the severity of these assessments will be recorded and carefully monitored during the study, worsenings do not need to be recorded as AEs unless the investigator judges it appropriate. Any treatment-emergent findings (i.e., findings that were not present prior to treatment or a worsening relative to the pretreatment baseline) outside of these assessments should be recorded as an AE.

Ophthalmoscopy: A new finding or a significant worsening (2 units or more) from baseline should be recorded as an AE.

VAS: Pain/discomfort will be assessed in the study eye. Since the severity of these assessments will be recorded and carefully monitored during the study, worsenings do not need to be recorded as AEs unless the investigator judges it appropriate.

AE Considerations: Additional exams may be scheduled as necessary to ensure the safety of the subjects during the study period. Subjects discontinued due to an AE should be seen for post-study follow-up visits, as needed. Adverse events considered related to study drug that have not resolved or stabilized by the final study visit will be followed during post-study follow-up visits at the discretion of the investigator until the incident has resolved or stabilized and will be documented in the source documents and AE eCRF. Where appropriate, additional written reports and documentation will be provided. Adverse events considered not related to study drug that have not resolved or stabilized by the final study visit will be noted as ongoing in the eCRF, followed at the discretion of the investigator, and recorded in the source documents.

Pregnancy: Although pregnancy is not considered an AE, any complication related to pregnancy would be considered an AE and recorded in the source documents and, if applicable, on the AE eCRF. If an SAE is associated with the pregnancy, the SAE should be reported on the SAE Report Form.

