4.2. Exclusion Criteria

The following are exclusion criteria for prospective study subjects to be confirmed from Day -14 – Day -2 (at Visit 1) prior to randomization:

1. Subject has any intraocular inflammation (cells and flare in the anterior chamber) or ocular pain (pain score of >0) in either eye prior to surgery.
2. Subject has any extraocular inflammation in the study eye prior to surgery (blepharitis is allowed if only scurf is present without any concurrent conjunctivitis or lid erythema/edema) or ongoing uveitis.
3. Subject has a history of diabetic retinopathy and/or previous vitrectomy in the study eye within the last 2 years prior to Screening which, in the investigator's opinion, is clinically significant and could impact the normal outcome of an uncomplicated cataract surgery.
4. Subject has a diagnosis of severe dry eye in the study eye.
5. Subject has any sign of iritis or scleritis in the study eye.
6. Subject has a history of glaucoma surgery in the study eye within the last 2 years prior to Screening.
7. Subject has a history of retinal surgery in the study eye within the last 2 years or plans to undergo retinal surgery in the study eye during the study period (from Screening through Day 32)

8. Subject has a history of Fuchs' dystrophy in the study eye.
9. Subject has guttata or chalazion in the study eye.
10. Subject has undergone radial keratotomy, photorefractive keratotomy, advanced surface ablation, corneal transplant, or LASIK in the study eye within the last 2 years prior to Screening.
11. Subject plans to undergo cataract surgery in the non-study (fellow) eye during the study period (from Screening through Day 32).
12. Subject plans to undergo additional ocular surgery (including femtosecond laser-assisted cataract surgery, minimally invasive glaucoma surgery, astigmatic keratotomy, limbal relaxing incision surgery, mechanical pupillary expanders, conjunctival incisions, and vitrectomy) in either eye during the study period (from Screening through Day 32).
13. Subject has a history of intraocular injections in the study eye within 6 months prior to Screening.
14. Subject has a history of herpes simplex infection in either eye.

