7. CONCOMITANT MEDICATIONS

Disallowed medications include:

- Any corticosteroid at least 15 days before surgery and throughout the duration of the study;
- Depot-corticosteroids in either eye at least 45 days before surgery and throughout the duration of the study;
- Administration of any nonsteroidal anti-inflammatory drugs (NSAIDs) including but not limited to topical, systemic (including sleep-aids containing NSAIDs), inhaled, or irrigation solution at least 1 week before surgery and throughout the duration of the study, with the exception of aspirin, where oral doses of 165 mg/day or lower are allowed;
- Ocular or systemic antihistamines (including sleep-aids containing an antihistamine), or mast cell stabilizers in either eye at least 1 week before surgery and throughout the study's dosing period;
- Triamcinolone in either eye at least 90 days before surgery and throughout the study's dosing period;
- Medications used to treat benign prostatic hyperplasia throughout the duration of the study;
- Inhaled, ingested, sublingual, transdermal or topical products containing marijuana, tetrahydrocannabinol (THC) or cannabidiol (CBD) at least 1 week before surgery and throughout the study's dosing period and for one day after the study's dosing period ends;
- Systemic pain relievers, analgesics (e.g., pregabalin, gabapentin, opioids) 14 days before surgery and throughout the duration of the study;
- Any supplement, prescribed medication or over-the-counter product that the investigator feels may interfere with the study parameters, including homeopathic remedies, analgesics, and pain medication.

During the study dosing period (Day -1 through Day 14), if the investigator determines that a rescue medication is necessary due to lack of efficacy (whether at a planned study visit or at an unscheduled visit), the subject should be discontinued from the study drug and the appropriate rescue medication prescribed. The subject should continue to be seen for all remaining study visits to assess safety and efficacy. This information must be recorded in the subject's source record and on the appropriate eCRF.

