10.2. Efficacy and Safety Variables

Primary Efficacy Endpoint(s): The primary efficacy endpoint will be the proportion of subjects with ACC grade of 0 (cell count=0) at Day 15. Subjects with an ACC grade of >0 at Day 15 or who receive rescue medication prior to Day 15 will be treated as failures. Last-observation-carried-forward (LOCF) will be used for the intent-to-treat (ITT) analysis.

Secondary Efficacy Endpoint: The secondary efficacy endpoint is the proportion of subjects who achieve a pain score of 0 at each post-surgical VAS (0-100 millimeter [mm] scale) assessment (Days 1, 8, 15, 22 and 32).

Safety Variables: AEs, BCVA, IOP, biomicroscopic and ophthalmoscopic findings.

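### The plan does not say whether a subject discontinued for an adverse event keeps the Day 15 visit; if not, LOCF sets that subject's ITT primary outcome, in rare cases from the pre-surgical screening reading

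*Combined protocol and SAP*

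**What the plan says.** Section 9 (AE Considerations) has one sentence on visits after an AE discontinuation: "Subjects discontinued due to an AE should be seen for post-study follow-up visits, as needed". It does not name what is being discontinued.

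Section 7 is explicit for another group. When rescue is needed for lack of efficacy during dosing, "the subject should be discontinued from the study drug and the appropriate rescue medication prescribed", and then "The subject should continue to be seen for all remaining study visits to assess safety and efficacy". Stopping drug and leaving the study are kept apart there, but only for that group.

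Section 8 schedules the slit-lamp examination that yields the ACC grade: it "will be conducted by a board-certified ophthalmologist at Screening Visit 1 (Day -14 to Day -2) and at Visit 3 through Visit 7" (Day 1 to Day 32). Nothing is said about subjects off drug. An early exit visit is named once, under ophthalmoscopy: "Ophthalmoscopy will be performed at Visit 7/Early Discontinuation Visit only if not performed at Visit 5". The plan does not say who has that visit or whether ACC is graded at it.

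The primary endpoint (Section 10.2) is the proportion with ACC grade 0 at Day 15. Subjects with a grade above 0 at Day 15 or "who receive rescue medication prior to Day 15 will be treated as failures". Stopping for an AE is not a failure event. For missing values, "Last-observation-carried-forward (LOCF) will be used for the intent-to-treat (ITT) analysis"; Section 10.4 applies this whatever the cause, and Section 10.6.1 confines it to ITT. Under Section 10.3, ITT is every randomized subject who has the surgery.

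**The concern.** Two readings of Section 9 are open. On one, the Section 8 schedule continues and Section 9 adds safety follow-up. On the other, the subject has left the study and the Day 15 examination is not done. Sites may differ, and a Day 15 ACC grade that was never taken cannot be recovered at analysis.

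On the second reading, the primary outcome of an unrescued subject comes from an earlier day. That may be Day 8, Day 1 or an exit or unscheduled examination. If there is no post-surgical reading, nothing in the LOCF rule stops the screening reading from being carried. Exclusion criterion 1 in Section 4.2 ("Subject has any intraocular inflammation (cells and flare in the anterior chamber") makes that reading cell-free, so an eye last graded before surgery would count as cleared after it.

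Scheduled pain, IOP and visual acuity assessments after the stop could be lost in the same way. Discretionary safety follow-up would remain, so it is the scheduled timing that is at risk.

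**Working it through.** The plan gives no figure to reproduce: no AE-stop rate, clearance rate, effect size or power. The check has two parts.

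**1. Who is affected.** All four conditions must hold:

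- the subject had surgery, and so is in ITT (Section 10.3);
- the subject stopped for an AE before Day 15;
- the subject was not rescued before Day 15 (rescued subjects are failures by rule, Sections 10.2 and 10.6.1);
- no Day 15 ACC grade was taken.

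The scheduled readings before Day 15 are Screening, Day 1 and Day 8 (Section 8). The screening reading is carried only if the Day 1 grade is also missing and there was no later or exit grade.

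**2. Size.** From the documents: 40 per arm (Section 2), and a two-sided z-test for proportions at 5% (Section 10.6.1). A pooled variance is assumed, because the plan does not specify one. One changed outcome moves an arm by 1/40 = 2.5 percentage points.

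Let d be the affected share of an arm, q the share of affected subjects clear at their last reading, and 0.30 the assumed true Day 15 success rate in both arms (no treatment effect):

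- arm rate = (1 − d) × 0.30 + d × q
- shift in an arm = d × (q − 0.30)

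Example with d = 0.15 (active) v 0.05 (vehicle) and q = 0.45. Active: 0.85 × 0.30 + 0.15 × 0.45 = 0.3225. Vehicle: 0.95 × 0.30 + 0.05 × 0.45 = 0.3075. The difference shifts by +1.5 points.

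Two-sided error is from exact binomial enumeration of the pooled z-test. All values of d and q are assumptions.

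| Affected, active v vehicle | q | Shift in difference (points) | Two-sided error |
|---|---|---|---|
| none | – | 0 | 4.8% |
| 15% v 5% | 0.15 | −1.5 | 5.1% |
| 15% v 5% | 0.45 | +1.5 | 5.0% |
| 7.5% v 2.5% | 0.15 | −0.75 | 4.9% |
| 7.5% v 2.5% | 0.45 | +0.75 | 4.9% |
| 5% v 2.5% | 0.15 | −0.375 | 4.9% |
| 5% v 2.5% | 0.45 | +0.375 | 4.8% |
| 5% v 5% | 0.15 or 0.45 | 0 | 4.8% to 4.9% |
| 15% v 5% (extreme q) | 0 | −3.0 | 6.0% |
| 15% v 5% (extreme q) | 1 | +7.0 | 9.9% |

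Swapping the arms reverses every sign. The two-sided figure partly hides direction. At 15% v 5%, the chance of a significant result favouring SURF-201 is 1.7% at q = 0.15 and 3.3% at q = 0.45, against 2.4% with no bias.

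A single subject changes the test result only close to the boundary. With assumed counts, 18/40 v 10/40 gives p = 0.061 and 19/40 v 10/40 gives p = 0.036.

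**The case against.** The best defence is that Section 9 does not set the visit schedule. Its next use of the follow-up wording concerns AEs still unresolved at the final study visit, so the sentence can be read as extra follow-up on top of the schedule. Sections 2 and 8 list the visits with no exception for subjects off drug. Sections 7 and 9 also cover different events and do not contradict each other. This stands as a fair reading, and it is why the point is an ambiguity and not an established loss of data. It does not close the gap: Section 9 leaves open what is discontinued, and Section 8 foresees early exit.

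Section 8 also writes Visit 7 and the early exit visit as one, and biomicroscopy is due at Visit 7. An exiting subject would therefore probably have an ACC grade. That stands too, and it makes a carried screening reading remote, though still not barred.

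Three stronger conclusions might be inferred, and the documents support none of them.

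- **That the primary test is materially biased.** The 9.9% figure needs a threefold imbalance between arms and every affected subject clear at an earlier reading when only 30% would be clear at Day 15. Nothing in the plan points to either, or shows what a realistic upper limit for AE stops would be.
- **That the bias favours SURF-201.** A carried early grade above 0 is a failure, so the direction is open.
- **That the per-protocol result would turn significant.** LOCF does not apply there, and the handling is simply unspecified. From 18/40 v 10/40, dropping an active failure gives 18/39 v 10/40, p = 0.049. Dropping an active success gives 17/39 v 10/40, p = 0.082, and dropping a vehicle failure gives 18/40 v 10/39, p = 0.072. One chosen example shows nothing.

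**Conclusion.** The concern holds as a minor one. The plan leaves open whether a subject stopped for an AE is still examined at Day 15. If the subject is not, LOCF determines the ITT primary outcome, with no bar on a pre-surgical reading that is cell-free by eligibility. The first gap could lead to uneven data collection across sites. The second could score a success that no post-surgical examination supports, but only in rare subjects.

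The expected effect is small and its direction unknown: 2.5 points per changed outcome, and two-sided error of about 4.8% to 5.1% outside extreme assumptions. These error rates rest on assumed AE-stop and clearance rates, a 30% success rate in both arms and a pooled z-test. The case for acting is that an uncollected Day 15 grade cannot be recovered and that prevention costs little.

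**What to change.** Reconcile Sections 7, 8 and 9 by separating stopping study drug from leaving the study. State that subjects who stop drug for any reason, including an AE, keep the scheduled assessments (ACC, VAS, IOP, BCVA) through Day 32 unless they withdraw consent.

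In Sections 10.2, 10.4 and 10.6.1, limit LOCF to post-surgical ACC readings and count a subject with none as a failure. Report by arm how many primary outcomes were imputed and why, with a missing-as-failure sensitivity analysis. That analysis is a check and not a replacement. It corresponds to q = 0, so at 15% v 5% affected it would itself shift the difference by −3.0 points.

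The cost is short wording changes, a few extra visits that are already on the schedule, and one table. The change concerns data collection and analysis only; it alters no treatment, rescue or stopping rule.
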